4.3.1.1 Changes from interim analysis to SAP-defined analyses

For TEAE two summary tables were presented as described in previous section with one modification: the first table was displaying all TEAE during the Double-Blind Period instead of limiting it TEAE with a relative TEAE start date less equal 84 days.

The definitions of AE of special monitoring were updated with the third SAP Amendment after the interim analysis. The interim analysis used the previous definition which is displayed in [Section 4.3.1.2](#). The interim analysis only displayed the overall number of AE of special monitoring by treatment group.

The baseline definition for CRP and hs-CRP measurements were updated with the fourth SAP Amendment after the interim analysis. The interim analysis used the previous definition: The last valid measurement before first dose of study drug (Visit 2) will be used as the Baseline value.

4.3.1.2 Search and selection criteria for AE of special monitoring for interim analysis

Following AEs are defined as TEAEs of special monitoring:

- Fungal infectious disorder
- Opportunistic infection (including TB)
- Malignant or unspecified tumor
- Malignant tumor
- Major cardiovascular event
- Haematopoietic cytopenias
- Neuropsychiatric events
- Inflammatory bowel disease
- Hypersensitivity and anaphylactic reaction

- Hepatic events

Fungal Infectious disorder

All TEAEs which code into the High Level Group Term (HLGT) of “Fungal infectious disorders” are classified as fungal infectious disorder.

Opportunistic infection

All TEAEs identified using UCB-defined search criteria as described in [Section 12.13](#).

Malignant or unspecified tumor

The search criteria is based on the Standardized MedDRA Query (SMQ) = “Malignant or unspecified tumours (SMQ)”.

Malignant tumor

The search criteria is based on the SMQ=“Malignant tumours (SMQ)”.

Major cardiovascular events

The major cardiovascular events are identified using the following UCB-defined search criteria:

- All serious TEAEs which code to a PT included in the Scope=Broad and/or Scope=Narrow groups of the following SMQs:
 - Haemorrhagic central nervous system vascular conditions (SMQ)
 - Ischaemic central nervous system vascular conditions (SMQ)
- All serious TEAEs which code to a PT included in the HLT “Ischaemic coronary artery disorders” except events coding to PT “Chest Pain” or “Chest discomfort”
- All serious TEAEs which code to a PT included in any of the following HLTs: “Heart Failures NEC”, “Left Ventricular Failures”, or “Right Ventricular Failures” and which also code to the SOC of “Cardiac Disorders” as Primary SOC.

Haematopoietic cytopenias

The search criteria is based on the SMQ = “Haematopoietic cytopenias”. The SMQ search should include all serious TEAEs which code to a PT included in the Scope=Broad and/or Scope=Narrow groups within the SMQ.

Neuropsychiatric events

The search criteria is based on the SMQ = “Depression and suicide/self-injury (SMQ)”. The SMQ search will include all TEAEs which code to a PT included in the Scope=Broad and/or Scope=Narrow groups within the SMQ.

Inflammatory bowel disease

All TEAEs which code into the HLT of “Colitis (excl infective)” are identified as inflammatory bowel disease.

Hypersensitivity reactions and anaphylactic reactions

Hypersensitivity reactions and anaphylactic reactions will be identified as follow:

- a) Hypersensitivity reactions: All TEAEs that either emerged on the same day as when a study medication injection reaction was received, or that emerged one day after a study medication injection was received, which code to a PT which contains the term “hypersensitivity” will be considered to be a hypersensitivity reaction and included in the summary table as such.
- b) Anaphylactic reactions: An algorithmic approach will be used to identify TEAEs that are considered to be anaphylactic reactions. PTs are separated into the 4 distinct categories (A, B, C, D) prior to the algorithmic approach being applied.

All TEAEs that either emerged on the same day as when a study medication injection reaction was received, or that emerged one day after a study medication injection was received, and which fulfill any of the 3 criteria described in [Section 12.14](#) will be included in the summary table.

Hepatic events

The search criteria is based on all TEAEs in the SMQ “Drug related hepatic disorders - comprehensive search (SMQ)”. Note that the following two sub-SMQs are to be excluded: “Liver neoplasms, benign (incl cysts and polyps)” and “Liver neoplasms, malignant and unspecified (SMQ)”.

The SMQ search should include all TEAEs (regardless of whether they have been judged as related to study medication or not) which code to a PT included in the Scope=Narrow group within each SMQ.

4.3.2 Interim analysis Week 48

After all enrolled subjects have completed the Week 48 or Early termination visit, a second interim analysis will be performed to analyze the key efficacy and safety data for the whole treatment period.

No separate SAP for that interim analysis will be provided. The interim analysis is a subset of the final analysis and will focus on the primary and secondary efficacy analysis. The TFL shells for the final analysis will be used.

The snapshot for the PA0008 interim analysis Week 48 will occur before all subjects have completed the PA0008 study. Specifically, subjects who do not enter the extension study will need to complete the SFU Visit, which occurs 20 weeks after the last dose of study treatment. The Week 48 interim database lock will be performed based on the last subject completing the Week 48 visit. It is anticipated that there will be some subjects still awaiting the SFU at that time. The number of subjects in the SFU period is expected to be low, and the minimal data to be collected from their SFU visits is not considered mandatory to evaluation of the key efficacy and safety objectives of the study.

4.3.2.1 Changes from interim analysis to SAP-defined analyses

The baseline definition for CRP and hs-CRP measurements were updated with the fourth SAP Amendment after the interim analysis. The interim analysis used the previous definition: The last valid measurement before first dose of study drug (Visit 2) will be used as the Baseline value.

4.3.2.2 Changes during interim analysis to SAP-defined analyses

At the time of the Week 48 interim it was discovered that the DBRS and ESS were defined incorrectly from the original intent. The original intent of the ESS analysis set was to have only those subjects that were eligible to receive rescue therapy, that went on to actually receive rescue therapy, with all other subjects remaining in the DBRS. As such, two extra sets, the cDBRS and cESS have been added. These analysis sets will correctly select out those subjects that were eligible and received rescue medication. For the final analysis, all outputs created on the DBRS and ESS will also be produced on the cDBRS and cESS to give full transparency of the difference. Further all outputs using the DBRS and ESS will be repeated on the DBS and this analysis will be used as the main analysis of the Dose-Blind as this analysis set is the most unbiased set.

4.4 Multicenter studies

The data from all centers will be pooled for the purposes of the analysis. There will be no formal statistical evaluation of the effect of center on the results obtained.

4.5 Multiple comparisons/multiplicity

In order to control for the overall Type I error rate, the pairwise comparisons of bimekizumab will be formally evaluated for statistical significance only if the primary efficacy analysis is statistically significant at the two-sided 5% level. In addition, the pairwise comparisons will follow a sequential testing sequence and the formal evaluation of statistical significance of each comparison is dependent upon the previous comparison achieving statistical significance at the two-sided 5% level. If the sequential testing fails to reach significance at a significance level of $\alpha=0.05$, then the pairwise testing will continue and the comparison are seen as non-significant. The p-values will be displayed as nominal p-values. More details can be found in [Section 8.1.3](#).

4.6 Use of an efficacy subset of subjects

The primary dose-response analysis and pairwise comparisons will be repeated for (1) all subjects in the PPS, and (2) for all subjects in the RS as a supportive analysis. The purpose is (1) to evaluate the effect of important protocol deviations on the analysis, and (2) to evaluate the consistency of the FAS with the intent-to-treat (ITT) principle.

4.7 Active-control studies intended to show equivalence

Not applicable.

4.8 Examination of subgroups

The following variables for subgroup analyses will be used:

- Age (<45 years, ≥ 45 to <65 years, ≥ 65 years)
- Gender (male, female)
- Geographic region (North America, Europe)
- BASDAI (<4 [mild disease]; ≥ 4 to ≤ 7 [moderate disease]; > 7 to ≤ 10 [severe disease])
- Prior TNF inhibitor exposure (yes, no)
- Treatment-emergent AbAb status (positive, negative)

- Extent of psoriasis involvement (<3%, ≥3% to <10%, ≥10%)
- hs-CRP level (≤ upper limit normal, > upper limit normal)
- Time since first diagnosis of PsA (< 2 years, ≥ 2 years)
- Body weight (<100 kg, ≥100 kg)

Subjects will be counted to have a positive treatment-emergent AbAb status in case the first AbAb positivity occurred up to Visit 7 (Week 12). The definition of first AbAb occurrence is described in [Section 9.2](#).

The derivation of time since first diagnosis of PsA is described in [Section 6.2](#).

5 STUDY POPULATION CHARACTERISTICS

5.1 Subject disposition

Summary tables of all subjects screened will be presented including reason for screen failures and disposition of subjects screened. The disposition of subjects screened will include the number of subjects included in each analysis set (ES, RS, SS, FAS, PPS, PK-PPS, PD-PPS, DBS, ESS, and DBRS) overall and by site.

The number and percentage of subjects who discontinued study medication, who discontinued the study, and who discontinued due to AEs will be summarized for subjects in the RS and DBS. The table using RS will analyze subjects for the complete study as well as the Double-Blind Period. Completed study is defined as completed the 12-week Double-Blind Period and the 36-week Dose-Blind Period including the safety follow-up visit. Subjects will be allocated to the treatment group at Baseline. The table using DBS will only summarize subjects in the Dose-Blind Period.

Study eligibility criteria will be listed and a separate listing of subjects who did not meet the eligibility criteria will be presented.

Subject disposition will be listed for all subjects screened and will include, inter alia, the following information: subject status, date of informed consent, randomization, first and last study medication, and primary reason for premature study termination. Listings of subject analysis sets, study and study medication discontinuation, and visit dates will be presented by subject including the relative study day (calculated as described in [Section 3.2.1](#)) for each visit

5.2 Protocol deviations

Important protocol deviations will be identified and classified by the deviation types. Following different important protocol deviation types will be classified: inclusion criteria deviation, exclusion criteria deviation, withdrawal criteria deviation, prohibited concomitant medication use, incorrect treatment or dose, treatment non-compliance, and procedural non-compliance.

Summary tables of the number and percentage of subjects with an important protocol deviation will be provided including a summary of subjects excluded from the PPS, PK-PPS, and PD-PPS due to important protocol deviations. Summary tables will be presented for FAS and Baseline treatment groups.

A listing of all important protocol deviations identified at the data evaluation meeting will be presented by subject for all subjects in the RS, and will include deviation type and description.

6 DEMOGRAPHICS AND OTHER BASELINE CHARACTERISTICS

6.1 Demographics

Tables with descriptive statistics (number of subjects, mean, SD, minimum, median, and maximum) and listings will be given for the demographic variables age (at time of informed consent), gender, racial group, ethnicity, weight at Screening, height at Screening, body mass index (BMI), country, and geographic region. Age and BMI will be summarized as a continuous variable and as categorical variables. Age will be combined based on the following categories: ≤ 18 , 19- <65 , ≥ 65 years (clinicaltrials.gov requirement), 18- <65 , 65- <85 , ≥ 85 years (EudraCT requirement), and 18- <45 , ≥ 45 - <65 , ≥ 65 years. BMI will be summarized based on the following categories: <25 , 25- <30 , ≥ 30 kg/m².

BMI in kg/m² is calculated based on the height (in m) and the weight (in kg) using the formula:

For adults:

$$BMI = \frac{Weight}{Height^2} \quad (5)$$

Even if they are available in the database, these variables are calculated during analysis (if applicable). These calculated values are used in the statistical analysis since they are considered more accurate.

A frequency table for Lifestyle will be presented as well as a corresponding listing. Data collected in the CRF for subject's childbearing potential and birth control will only be listed.

The summary tables will be performed on the SS and repeated using the FAS and the DBS. If the SS and FAS analysis sets are identical the summaries will not be repeated. The Listing will be provided for all subjects screened, except the Lifestyle listing will use the RS.

6.2 Other Baseline characteristics

PsA history will be summarized for subjects in the FAS and SS including the time since first diagnosis of PsA, age at first diagnosis date, and PsA subtype (polyarticular – symmetric arthritis, oligoarticular – asymmetric arthritis, distal interphalangeal, joint predominant, spondylitis predominant, arthritis mutilans). Time since first diagnosis will be summarized as a continuous variable and as categorical variables based on following categories: <2 , ≥ 2 years. The history will be listed for all subjects in the RS.

Time since first diagnosis of PsA will be calculated as:

$$\begin{aligned} & \text{Time since first diagnosis (years)} \\ & = \frac{\text{Date of Informed Consent} - \text{Date of diagnosis} + 1}{365.25} \quad (6) \end{aligned}$$

If the date of diagnosis is partial, it should be imputed to the most recent feasible date (ie, last day of the month if only day is missing, or the last day of the year if day and month are missing).

Age at first diagnosis will be calculated as:

$$\text{Age at first diagnosis} = \frac{\text{Date of first diagnosis} - \text{Date of birth}}{365.25} \quad (7)$$

These formulas may result in incorrect ages after rounding if the birth day falls on the date of first diagnosis. In that case the age is calculated as the number of years between the year of birth and the year of the randomization visit. The age for individual subjects is presented with 1 decimal. The rounding is done downwards. For subjects enrolled at German sites, only the year of birth may be entered into the eCRF for this study. For these subjects age will be calculated after imputing their date of birth to be 01 Jan XXXX.

Baseline characteristics (including Scores relevant for inclusion and exclusion criteria) will be summarized by treatment group and overall for FAS, SS, and DBS. Following variables will be summarized:

- TJC
- SJC
- hs-CRP
- Rheumatoid factor
- Anti-CCP antibodies
- Prior NSAID therapy, and prior anti-TNF therapy
- Psoriasis BSA
- Nail psoriasis
- Dactylitis
- NSAID therapy
- Synthetic DMARDs
- MTX
- Sulfasalazine
- Hydroxychloroquine

A rheumatoid factor value < 15 IU/mL is defined as negative and a value ≥ 15 IU/mL is defined as positive. Anti-CCP antibodies negative is a value < 5 U/mL and a value ≥ 5 U/mL is defined as positive.

For hs-CRP following rules will be applied:

- If Baseline hs-CRP values are missing, then take the Screening hs-CRP values.
- If Screening hs-CRP values are missing, then take the median hs-CRP values.

The corresponding listings will be presented for the RS.

6.3 Medical history and concomitant diseases

Medical history and ongoing medical conditions will be summarized by MedDRA SOC and PT by treatment and overall including the number and percentage of subjects with each condition. The denominator for the percentages will be the number of subjects in the SS and FAS for each treatment or overall.

Medical history and ongoing medical conditions will be listed by treatment and subject including the reported term, PT, and SOC for the RS. The start date (month and year only) and end date (or ongoing if applicable) will also be included in the listing. A glossary of all medical history conditions will also be presented including the reported term, PT and SOC.

6.4 Prior and concomitant medications

Prior medications include any medications that started and ended prior to the start date of study medication. Concomitant medications are medications taken at least one day in common with the study medication dosing period. For bimekizumab, the dosing period is typically from the date of first dose up to (but not including) one dosing interval post last dose. Thus, a concomitant medication is any medication whose start date is on or after the date of first study medication and prior to the date of last study medication administration + 28 days (1 dosing interval), or whose stop date is either missing, or on or after the date of first study medication administration.

In the case of missing data, the classification of medications as prior or concomitant will be performed as described in [Section 4.2.3](#).

The number and percentage of subjects taking prior medications will be summarized by treatment group, overall and by anatomical therapeutic chemical (ATC) class, presenting Anatomical Main Group (ATC Level 1), Pharmacological Subgroup (ATC level 3), and PT.

The number and percentage of subjects taking concomitant medications will be summarized similarly. Tables for prior and concomitant medications will be presented for SS and FAS.

Prior and concomitant medications will be listed by treatment and subject for RS.

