#### **8.6 Safety Follow-Up Visit (20 weeks [-3 days/+7 days] after the final dose)**

- Record concomitant medications.
- Record AEs.
- eC-SSRS
- HADS
- Administer the PsAQoL.
- Determine the BASDAI.
- Administer the HAQ-DI.
- Administer the SF-36.
- Administer the PGADA.
- Administer the PtAAP.
- Administer the PsAID-9.
- Administer the tuberculosis questionnaire.
- Measure temperature, pulse, and BP.
- Measure weight.
- Perform a physical examination, including an evaluation for signs and symptoms of active TB and risk for exposure to TB.
- Perform TJC/SJC.

- Determine BSA affected by PSO using the BSA palm method.
- If the BSA affected by PSO was  $\geq 3\%$  at Baseline/Day 1, determine the PASI.
- Determine the MASES.
- Determine the LDI.
- Perform the PhGADA.
- Perform an ECG.
- Collect samples for hematology/biochemistry/urinalysis.
- Collect blood sample for hs-CRP.
- Perform a urine pregnancy test if the subject is a woman of childbearing. This requirement also applies to women of childbearing potential with infrequent or irregular menstrual cycles and women during menopause. Natural menopause is recognized to have occurred after 12 consecutive months of amenorrhea, for which there is no other obvious pathological or physiological cause.
- Collect a blood sample for bimekizumab plasma concentrations and anti-bimekizumab antibody detection.
- Perform an IGRA tuberculosis test.
- Record visit in the IXRS.

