13.5.2 Modification and changes

Text added for Section 4.2.1 Handling of missing data for efficacy analysis

The imputation model will be applied for each treatment group separately. However, in the event there are computational challenges with the imputation model (eg, due to a standard deviation of 0 for responses of a given imputation), it is acceptable to modify the imputation model to include treatment as a variable in the model rather than running a separate model for each treatment group. It should be noted that doing so assumes that treatment does not interact with any of the other variables in the imputation model.

Section 6.4 Prior and concomitant medications

Prior medications include any medications that started and ended prior to the start date of study medication. Concomitant medications are medications taken at least one day in common with the study medication dosing period. For bimekizumab, the dosing period is typically from the date of first dose up to (but not including) one dosing interval post last dose. Thus, a concomitant medication is any medication whose start date is on or after the date of first study medication and prior to the date of last study medication administration + 28 days (1 dosing interval), and whose stop date is either missing, or on or after the date of first study medication administration.

...

Has been changed to

Prior medications include any medications that started and ended prior to the start date of study medication. Concomitant medications are medications taken at least one day in common with the study medication dosing period. For bimekizumab, the dosing period is typically from the date of first dose up to (but not including) one dosing interval post last dose. Thus, a concomitant medication is any medication whose start date is on or after the date of first study medication and prior to the date of last study medication administration + 28 days (1 dosing interval), **or** whose stop date is either missing, or on or after the date of first study medication administration.

...

Section 7 Measurements of treatment compliance

...

A summary of percent treatment compliance categorized as $\leq 80\%$ and $> 80\%$ will be provided by treatment group for the overall treatment period as well as for Double-Blind treatment period.

A by-subject listing of treatment compliance will be provided.

Has been changed to

...

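### The 28-day limit in the concomitant-medication rule never takes effect, so drugs first taken during safety follow-up count as concomitant

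*SAP*

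**What the plan says.** SAP section 6.4 gives the definition first: "Concomitant medications are medications taken at least one day in common with the study medication dosing period". It then bounds the period: "the dosing period is typically from the date of first dose up to (but not including) one dosing interval post last dose".

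The next sentence is presented as following from that definition. It accepts a drug whose start date lies from first dose up to, but not including, last dose + 28 days, "or whose stop date is either missing, or on or after the date of first study medication administration".

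The companion definition is "Prior medications include any medications that started and ended prior to the start date of study medication".

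As background, SAP section 13.5.2 shows that Amendment 5 changed the connector. The superseded clause read "and whose stop date is either missing, or on or after the date of first study medication administration".

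Medication data are collected well beyond the dosing period. Protocol section 8.6 (Safety Follow-Up Visit, 20 weeks after the final dose) includes the instruction "Record concomitant medications". Under Protocol section 5.1.5 that visit applies to subjects who complete without entering the extension study or who discontinue early.

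**The concern.** The definition and the rule meant to implement it disagree within one paragraph. The definition requires overlap with dosing. The rule puts no upper limit on the start date of a drug that qualifies through its stop date, and every drug started after first dose qualifies that way.

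The subjects most exposed are those who stop bimekizumab and go on to something else. Protocol section 5.1.4 requires bimekizumab to be discontinued before another biologic is used. A replacement biologic first given 28 days or more after the last dose does not overlap the SAP's dosing period, yet it would appear in the concomitant-medication tables for the SS and FAS. A reader could take that as combined use.

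**Working it through.** There is no plan figure to reproduce; this is a check of a classification rule.

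**Notation.** F = date of first dose, L = date of last dose. From SAP 6.4:

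- Condition A: F ≤ start < L + 28
- Condition B: stop missing, or stop ≥ F
- Current rule: A or B
- Overlap with the dosing period: start < L + 28 and B

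**Step 1: the rule reduces to B.** Suppose A holds. Then start ≥ F. The stop date is either missing or no earlier than the start, so stop ≥ F, and B holds. A therefore implies B, and *A or B* is the same as B. The last dose + 28 days limit appears only in A, so it never changes a classification.

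**Step 2: enumeration.** Set F = day 0. Take every start day from 60 days before F to L + 147 (the Safety Follow-Up Visit at 140 days plus its 7-day upper window), with every possible stop day and a missing stop. Two cases: last dose at Week 44 (day 308) and at Week 8 (day 56).

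| Dates of the drug | Overlaps dosing | Current rule (A or B) | Superseded rule (A and B) | Proposed rule | Date pairs, Week 44 | Date pairs, Week 8 |
|---|---|---|---|---|---|---|
| Started and stopped before F | no | no | no | no | 1,830 | 1,830 |
| Started before F; stop missing or ≥ F | yes | yes | **no** | yes | 27,420 | 12,300 |
| F ≤ start < L + 28 | yes | yes | yes | yes | 97,272 | 13,734 |
| Start ≥ L + 28 | no | **yes** | no | no | 7,380 | 7,380 |
| Total | | | | | 133,902 | 35,244 |

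Hand checks:

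- Last row: there are 120 start days, L + 28 to L + 147. Each allows from 1 to 120 stop days plus a missing stop, so 120 × 121 / 2 + 120 = 7,380.
- Second row, Week 44: 60 start days × (456 stop days + 1 missing) = 27,420. Week 8: 60 × (204 + 1) = 12,300.

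These count possible date pairs and do not estimate how often each occurs. They show that the current rule misclassifies every start after the dosing period and nothing else. The superseded rule misclassified every baseline drug continued into treatment, leaving it neither prior nor concomitant.

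**Step 3: length of the affected window.** From last dose + 28 to the Safety Follow-Up Visit at last dose + 140: 140 − 28 = 112 days, or 112 / 140 = 80% of follow-up. With the visit window of −3 to +7 days, the range is 109 to 119 days. For a subject whose last dose is at Week 44, 112 days is 25% of the 308 + 140 = 448 days from first dose to that visit.

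**Step 4: does another section restore the limit?** SAP section 4.2.3 only imputes partial dates. It leaves a completely unknown stop date missing, which itself satisfies B. No upper limit on the start date was found elsewhere.

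**The case against.** The best defence is that the governing definition stands in the same paragraph and the faulty sentence only restates it, so a programmer could recover the intent. The documents do not show which version was coded. That is fair, but the rule is the part written as programmable conditions, and Amendment 5 edited it deliberately.

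A second defence is that the sponsor wanted a two-way split. The current rule is in fact the exact complement of the prior-medication definition. But the SAP does not say so, and a dosing period with a 28-day cut-off would then serve no purpose.

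Several limits on consequence do stand:

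- The 80% is a share of follow-up days, and only for subjects who have the Safety Follow-Up Visit. SAP section 4.3.2 expects few subjects still in follow-up at the Week 48 lock. For extension entrants last dosed at Week 44, the Week 48 visit falls at about last dose + 28 days, so their window is nominally nil.
- A biologic started within 28 days of the last dose is concomitant under the SAP's own definition. Only later starts are misclassified.
- Baseline therapy (SAP 6.2) and rescue medication (SAP 6.5) are summarised separately, and listings show dates as recorded.
- The change to *or* cured a real gap for continuing baseline drugs. The fault is the missing upper limit on the start date.

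**Conclusion.** The concern holds. As written, the rule classes every drug started on or after last dose + 28 days as concomitant, contrary to the definition it claims to implement. The affected window is nominally 112 days (109 to 119) for each subject who reaches the Safety Follow-Up Visit. The number of drugs or subjects affected cannot be derived from the documents.

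This assumes that the rule is programmed as worded and that drugs started in follow-up are recorded with their dates, as Protocol 8.6 provides.

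The importance is low. Only the concomitant-medication summaries and listing labels are affected. The primary ACR50 analysis does not use this classification, and exclusion from the PPS rests on important protocol deviations before Week 12 (SAP 3.4).

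**What to change.** Replace the working rule in SAP section 6.4 with: a medication is concomitant if its start date is before the date of last study medication + 28 days **and** its stop date is either missing or on or after the date of first study medication. There should be no lower bound on the start date. This keeps baseline drugs that continue into treatment and excludes all 7,380 post-period date pairs in the enumeration. Do not simply change *or* back to *and*.

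Drugs started at or after last dose + 28 days will then be neither prior nor concomitant. Add a few words saying how they are shown, for example listed under a follow-up label. If the sponsor does want a two-way split instead, the definition and the 28-day period should be removed so that the text agrees with the rule.

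The cost is one SAP sentence and one programming condition. The imputation rules in section 4.2.3 can stay as they are.
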